7.7 Performance and Safety Endpoints, Variables and Measurements

7.7.1 Patient Characteristics

Date of Birth (DOB), Race, Sex, Smoking Status, County/Region

7.7.2 Objectives

The aims of this study are to summarize and compare the incidence of clinical events and pro-inflammatory cytokine levels in patients randomized to use of gammaCore Sapphire plus standard of care vs standard of care alone in patients hospitalized for CoViD-19. In addition, this study is intended to demonstrate the safety of gammaCore Sapphire use in patients hospitalized for CoViD-19.

Specific clinical events to be summarized include, but are not limited to:

- Changes in oxygen support requirements (no oxygen support, low-flow oxygen support, nasal high-flow oxygen support, noninvasive mechanical ventilation, and invasive mechanical ventilation)
- Changes in O₂ saturation
- PaO₂/FiO₂ ratio
- Proportion of subjects requiring mechanical ventilation
- Days to onset of mechanical ventilation
- Live discharge from the hospital
- Patient length of stay
- Mortality
- Shortness of Breath
- Clinical improvement Scale

Specific laboratory measurements to be summarized include, but are not limited to:

- TNF- α
- IL-1 β
- IL-6
- CRP
- Ferritin
- D Dimer
- Pro-Calcitonin
-

7.7.3 Safety Variables and Measurements

The primary safety measure for this study is the incidence and occurrence of SAEs related to the study treatments.

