One treatment is defined as 2 consecutive doses (stimulations). Each dose delivers a 2-minute stimulation. One dose is applied to the left side of the neck, then one to the right. If shortness of breath (SOB) persists 20 minutes after start of first treatment, administer a second treatment. If the additional treatments do not appear to be providing benefit/relief of symptoms (as per patient or physician discretion) there is no need to continue with additional acute treatments. However, if it there appears to be benefit, the patient can administer more as needed. The patients can receive up to 9 acute treatments (or 18 stimulations) per day.

SoC: No Administration of gammaCore®

INCLUSION AND EXCLUSION CRITERIA:

Inclusion Criteria

All patients must meet the following inclusion criteria to be included in this study:

1. Patients (age 18 years and older) who have tested positive or suspected/presumed positive for CoViD-19 (PCR real time test)
2. Patients with cough, shortness of breath or respiratory compromise (RR>24/min, increased work of breathing.)
3. O₂ Saturation less than or equal to 96% on room air or sensation
4. Agrees to use the gammaCore Sapphire device as per protocol and to follow all of the requirements of the study including recording required study data
5. Permission for early am blood draw to freeze for subsequent lab tests and sequencing as related to CoViD-19 sequelae
6. Patient is able to provide signed and witnessed Informed Consent

Exclusion Criteria

Patients meeting any of the following criteria cannot be included in this research study:

1. On home/therapy oxygen (i.e. for COPD patients) at baseline prior to development of CoViD-19
2. Already using gammaCore® (nVNS) for other medical conditions
3. A history of aneurysm, intracranial hemorrhage, brain tumors, or significant head trauma
4. Known or suspected severe atherosclerotic cardiovascular disease, severe carotid artery disease (e.g., bruits or history of transient ischemic attack or cerebrovascular accident), congestive heart failure, known severe coronary artery disease, myocardial infarction documented within past 90 days, or current or recent history of life-threatening arrhythmia (sustained ventricular tachycardia, ventricular fibrillation, second or third-degree heart block, uncontrolled atrial fibrillation or

uncontrolled atrial flutter)

5. Patients with clinically significant hypertension, hypotension, bradycardia, or tachycardia (as per investigator discretion)

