7.8.4 Reporting of Adverse Events/Adverse Device Effects

7.8.4.1 Methods for Eliciting Adverse Events/Adverse Device Effects

All patients will be carefully monitored for the occurrence of AEs during the investigation period from the run-in to the completion of follow up. The Clinical Investigator will collect AE information using non-leading questions such as "have you experienced any new health problems or worsening of existing conditions". Events directly observed or spontaneously volunteered by patients will also be recorded.

Clearly related signs, symptoms and abnormal diagnostic procedure results should be grouped together and reported as a single diagnosis or syndrome whenever possible.

All AEs including but not limited to events reported by the patient or reported in response to an open question by the Clinical Investigator or member of this team, which fall into any of the above definitions must be recorded as an AE in the CRF and should include the following information.

- Brief description of the event (diagnosis)
- Start date (and time, if relevant)
- Stop date (and time, if relevant) (or resolution)
- Severity
- Action taken regarding the medical device
- Opinion on causality
- Seriousness
- Outcome

Severity

Severity describes the intensity of an event and will be assessed as:

Mild

The AE does not interfere in a significant manner with the patient's normal functioning level. It may be an annoyance.

Moderate

The AE produces some impairment of function but not hazardous to health. It is uncomfortable and/or an embarrassment.

Severe

The AE produces significant impairment of functioning or incapacitation and/or it is a hazard to the patient.

If an AE changes in severity, it should be reported as an AE of new severity but with the same description.

Causality (Adverse Device Effects/ADE)

Causality will be assessed as:

- Related (definitely, possible or probable) - A causal relationship between the clinical investigational medical device and the AE is at least a reasonable possibility, i.e. there is evidence or argument suggesting a causal relationship.
- Not related - There is no indication that the AE was caused by the clinical investigational medical device.

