7.10.1.6 Adverse Events/Adverse Device Effects

Device-related serious adverse events will be tabulated. The overall incidence of device-related serious adverse events will be summarized and presented as a proportion and respective 95% exact binomial confidence interval. Additionally, an overview of events, to include total numbers of events, and total number of subjects with events will be tabulated and presented for all AEs, serious AEs, and device-related AEs and device-related serious AEs, as well as deaths. Events will be presented overall and by study arm.

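### The lead safety measure, device-related SAEs, has no comparator, and the plan commits to no between-arm estimate for all-cause SAEs or deaths

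*Combined protocol and SAP*

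**What the plan says.** Section 7.7.3 is a single sentence: "The primary safety measure for this study is the incidence and occurrence of SAEs related to the study treatments". Section 7.10.1.6 turns it into an analysis: "The overall incidence of device-related serious adverse events will be summarized and presented as a proportion and respective 95% exact binomial confidence interval". The same section adds an overview, "presented for all AEs, serious AEs, and device-related AEs and device-related serious AEs, as well as deaths", and says "Events will be presented overall and by study arm". That overview consists of numbers of events and of patients with events; no difference between arms is specified.

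Section 7.8.4.1 has the case report form record an "Opinion on causality". An event is related if "A causal relationship between the clinical investigational medical device and the AE is at least a reasonable possibility", a category that includes possible relationships, and not related if "There is no indication that the AE was caused by the clinical investigational medical device". Both definitions refer to the device only. The control arm in the synopsis reads "SoC: No Administration of gammaCore", and no sham is described.

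Four other places bear on the point:
- Section 7.7.2 says the study is meant to demonstrate the device's safety, and lists ventilation and mortality among the outcomes compared between arms.
- Section 7.10.1.1 puts every patient entering the study in the safety population and analyses it by treatment actually received.
- Section 7.10.1.2 makes all comparisons nominal and allows, without requiring, confidence intervals.
- Section 7.2.1.5 ends participation at discharge, at mechanical ventilation, or when the patient cannot continue.

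**The concern.** A randomised control group lets harm be estimated without deciding, case by case, what caused each event. The lead safety measure here depends entirely on that decision. The person deciding apparently knows the arm: the documents do not call the trial open-label, but with no sham the device is visible at the bedside, and no masked or independent causality review is described.

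In patients hospitalised with COVID-19, a device effect that worsened breathing could resemble the disease. If such events were put down to COVID-19, the lead measure would not register them however unevenly they fell between the arms. The evidence would then sit in descriptive tables for which the plan promises no estimate and no interval.

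**Working it through.** The plan states no SAE rate, power or safety margin, so there is no figure of its own to reproduce. The input from the plan is up to 60 patients, 30 per arm (7.4.1). All event counts and rates below are assumptions.

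**1. Who can have the event.** Sections 7.8.4.1 and 7.10.1.6 define the event as a device-related SAE, and the synopsis gives controls no device. A control who never uses it contributes zero by definition, and one who did use it would be analysed as treated under 7.10.1.1. The measure is in effect a single-arm proportion. The plural in 7.7.3 (study treatments) could be read to include standard of care, but no causality category exists for that, so the device reading is the workable one.

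**2. Which denominator.** Section 7.10.1.6 asks for an overall incidence, and the safety population contains both arms. With no events, the upper exact 95% limit is 1 - 0.025^(1/n):
- device-exposed patients only, n = 30: 1 - 0.025^(1/30) = 11.6%
- both arms pooled, n = 60: 1 - 0.025^(1/60) = 6.0%

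With one event the exact results are 1/30 = 3.3% (0.1% to 17.2%) and 1/60 = 1.7% (0.04% to 8.9%). Pooling halves the apparent rate by adding 30 patients who cannot have the event.

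**3. What a by-arm estimate would show.** Assume all-cause SAEs in 9/30 device and 6/30 control patients, none judged related. The lead measure gives 0/30 (0 to 11.6%) or 0/60 (0 to 6.0%). For the difference, the Wilson 95% limits are 16.7% to 47.9% for 9/30 and 9.5% to 37.3% for 6/30. Newcombe's method combines them, with d = 0.300 - 0.200 = 0.100:
- lower: 0.100 - sqrt[(0.300 - 0.167)² + (0.373 - 0.200)²] = 0.100 - 0.218 = -0.118
- upper: 0.100 + sqrt[(0.479 - 0.300)² + (0.200 - 0.095)²] = 0.100 + 0.207 = +0.307

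So the difference is +10 points (-12 to +31). With 12/30 against 6/30 it is +20 points (-3 to +41), and the lead measure is still zero if none is judged related.

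**4. Precision to expect.** With equal assumed rates and 30 per arm, the Newcombe half-width is 16.9 points at 10%, 20.2 at 20% and 22.3 at 30%. A two-sided 5% test would have 80% power only for increases of about 28 points from a control rate of 5%, 31 from 10%, 34 from 20% and 36 from 30%. The comparison can be an estimate; it cannot be a powered test.

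**The case against.** The strongest reply is that the comparison already exists. Section 7.10.1.6 tabulates all SAEs and deaths by arm. Section 7.7.2 compares oxygen support, ventilation and mortality between arms, which is where a harm that worsened COVID-19 would be expected to show, with no causality judgement. Section 7.10.1.2 permits intervals, and sections 7.10.1 and 7.10.1.3 leave detail to a separate SAP. A data safety monitoring board reviews adverse events quarterly (7.9.6). With every comparison nominal and no decision rule, the label of primary measure decides little.

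Most of this stands. A reader might infer that the randomised safety comparison is missing from the plan; it is not. What remains is narrower. Permission to present an interval is not a commitment, the clinical outcomes do not cover other kinds of SAE, and the one safety result with a promised interval is the one without a comparator.

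A reader might also take the single SAE in the first 20 patients, judged unrelated (7.10.4), as a sign of misattribution. The section gives neither the arm nor the type of event; had the patient been a control, unrelated would follow by definition. Because a possible relationship counts as related, the bar is also low. That COVID-like events would be called unrelated is a plausible risk, not something the documents show.

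Finally, the proposed interval would not have established the harm illustrated above, since -12 to +31 includes zero. That is true. Its value is that it states the uncertainty, which a zero count with no comparator does not.

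**Conclusion.** The point holds in this form: the lead safety measure has no comparator, it rests on a device-only causality opinion apparently formed with knowledge of the arm, and the plan commits to no between-arm safety estimate. For a study intended to demonstrate safety, this should be changed.

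Two sizes matter. With zero related events the upper limit is 11.6% or 6.0% depending only on the denominator, which section 7.10.1.6 leaves open. And an all-cause difference of 10 or 20 points could sit behind that zero. The second rests on assumed counts and on no event being judged related; the first needs only 30 patients per arm and no device use by controls.

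Dropping device-related SAEs from the lead position altogether is not required. They answer a different question and can stand beside the all-cause comparison.

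**What to change.** 1. In 7.7.3 and 7.10.1.6, add as a co-lead safety measure the proportion of patients with at least one SAE of any cause, including death, by arm, with the risk difference and its 95% Newcombe interval. Describe it as a nominal estimate, in line with 7.10.1.2.
2. Keep device-related SAEs with the exact interval, with device-exposed patients as the denominator, and align the wording of 7.7.3 with that of 7.10.1.6.
3. Reconcile the by-arm analysis with the as-treated rule in 7.10.1.1, for example by reporting it by randomised arm alongside as treated.
4. State one SAE and death window and apply it to both arms. Participation ends at discharge or ventilation (7.2.1.5), so observation time can differ between arms. The 30-day death reporting rule in 7.8.5 runs from receipt of the study product, which leaves its start unclear for controls. State also whether transition to ventilation is itself counted as an SAE.

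Items 1 to 3 cost protocol and SAP wording, since 7.10.1.6 already tabulates all SAEs and deaths by arm. Item 4 may need some data collection after ventilation or discharge if a fixed window is chosen. The statistical price is noise: all-cause events are less specific than related ones, and the interval will be about ±17 to ±22 points at assumed rates of 10% to 30%.

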7.7.4 Other Variables and Measurements

Comorbidities known to influence course of CoViD-19 including asthma or other underlying pulmonary disorders, diabetes and cardiac disease will be recorded.

7.7.5 Appropriateness of Measurements

The evaluative measurements include changes in oxygen support, O2 saturation and shortness of breath, the need and onset of mechanical ventilation, clinical improvement assessment and mortality. We will also correlate these with cytokine suppression. It is possible that those who have a drop, or do not have an increase in cytokine activation will have a higher survival and lower need for oxygen requirements and/or mechanical ventilation. These will permit evaluation of the objectives for the study.

The safety measurements are typical for a clinical trial and permit evaluation of the safety of the device.

7.8 Adverse Events/Adverse Device Effects and Device Deficiencies

The definitions and procedures for reporting adverse events (AE), adverse device effects (ADE), serious adverse events (SAE), serious adverse device effects (SADE) and are presented in the sections below. It is of utmost importance that all staff involved in the investigation are familiar with the definitions and procedures and it is the responsibility of the Clinical Investigator to ensure this.

7.8.1 Adverse Event/Adverse Device Effect Definitions

Adverse Event

Any untoward or unfavorable medical occurrence in a human subject, including any abnormal sign (for example, abnormal physical exam or laboratory finding), symptom, or disease, temporally associated with the subject's participation in the research, whether or not considered related to the subject's participation in the research

Adverse Device Effect

Adverse event related to the use of an investigational medical device.

Note 1: This definition includes any event resulting from insufficiencies or inadequate instructions for use, deployment, implantation, installation, or operation, or any malfunction of the investigational medical device.

Note 2: This definition includes any event that is a resulting from a user error or from intentional misuse of the investigational medical device.

7.8.2 Serious Adverse Event/Serious Adverse Device Effect/Unanticipated Adverse Device Effect Definitions

Serious Adverse Event

An adverse event is considered serious and should be reported to IRB when the patient outcome is:

- **Death**
- **Life-threatening** - the patient was at substantial risk of dying at the time of the adverse event, or use or continued use of the device or other medical product might have resulted in the death of the patient.
- **Hospitalization (initial or prolonged)** - admission to the hospital or prolongation of hospitalization was a result of the adverse event. Emergency room visits that do not result in admission to the hospital should be evaluated for one of the other serious outcomes (e.g., life-threatening; required intervention to prevent permanent impairment or damage; other serious medically important event).
- **Disability or Permanent Damage** - if the adverse event resulted in a substantial disruption of a person's ability to conduct normal life functions, i.e., the adverse event resulted in a significant, persistent or permanent change, impairment, damage or disruption in the patient's body function/structure, physical activities and/or quality of life.
- **Congenital Anomaly/Birth Defect** - suspected exposure to a medical product prior to conception or during pregnancy may have resulted in an adverse outcome in the child.
- **Required Intervention to Prevent Permanent Impairment or Damage (Devices)** - medical or surgical intervention was necessary to preclude permanent impairment of a body function, or prevent permanent damage to a body structure, either situation suspected to be due to the use of a medical product.
- **Other Serious (Important Medical Events)** - the event does not fit the other outcomes, but the event may jeopardize the patient and may require medical or surgical intervention (treatment) to prevent one of the other outcomes. Examples include allergic bronchospasm (a serious problem with breathing) requiring treatment in an emergency room, serious blood dyscrasias (blood disorders) or seizures/convulsions that do not result in hospitalization. The development of drug dependence or drug abuse would also be examples of important medical events.

Serious Adverse Device Effect

A SADE is an ADE that results in any of the consequences characteristic of an SAE or that might lead to any of these consequences if suitable action is not taken, if intervention is not made or if circumstances are less opportune.

7.8.3 Unanticipated serious adverse device effect (USADE)

Serious adverse device effect which by its nature, incidence, severity or outcome has not been identified in the current version of the risk analysis report.

Note: Anticipated serious adverse device effect (ASADE) is an effect which by nature, incidence, severity or outcome has been identified in the risk analysis report.

7.8.4 Reporting of Adverse Events/Adverse Device Effects

7.8.4.1 Methods for Eliciting Adverse Events/Adverse Device Effects

All patients will be carefully monitored for the occurrence of AEs during the investigation period from the run-in to the completion of follow up. The Clinical Investigator will collect AE information using non-leading questions such as "have you experienced any new health problems or worsening of existing conditions". Events directly observed or spontaneously volunteered by patients will also be recorded.

Clearly related signs, symptoms and abnormal diagnostic procedure results should be grouped together and reported as a single diagnosis or syndrome whenever possible.

All AEs including but not limited to events reported by the patient or reported in response to an open question by the Clinical Investigator or member of this team, which fall into any of the above definitions must be recorded as an AE in the CRF and should include the following information.

- Brief description of the event (diagnosis)
- Start date (and time, if relevant)
- Stop date (and time, if relevant) (or resolution)
- Severity
- Action taken regarding the medical device
- Opinion on causality
- Seriousness
- Outcome

Severity

Severity describes the intensity of an event and will be assessed as:

Mild

The AE does not interfere in a significant manner with the patient's normal functioning level. It may be an annoyance.

Moderate

The AE produces some impairment of function but not hazardous to health. It is uncomfortable and/or an embarrassment.

Severe

The AE produces significant impairment of functioning or incapacitation and/or it is a hazard to the patient.

If an AE changes in severity, it should be reported as an AE of new severity but with the same description.

Causality (Adverse Device Effects/ADE)

Causality will be assessed as:

- Related (definitely, possible or probable) - A causal relationship between the clinical investigational medical device and the AE is at least a reasonable possibility, i.e. there is evidence or argument suggesting a causal relationship.
- Not related - There is no indication that the AE was caused by the clinical investigational medical device.

7.8.4.2 Follow-up of Patients with Adverse Events

Any AE that is ongoing when the patient is withdrawn from the investigation should be followed-up until the AE is resolved or the Clinical Investigator decides that the AE is stable and needs no further follow-up. The date when the Clinical Investigator considers one of these outcomes to have occurred for the last ongoing AE for a patient will be considered the last visit for this patient, and the outcome should be recorded in the CRF.

7.8.5 Reporting of Events

INTERNAL: REPORTABLE EVENTS THAT OCCUR AT THE PI's RESEARCH SITE or are ASSOCIATED WITH THE PI			
Event	Examples (not all-inclusive)	How to Report	Report Timeframe
Serious Adverse Event (SAE)	
 ◦ Pneumonia resulting from study drug administration ◦ Significant allergic reaction resulting from study drug(s) ◦ Cardiovascular event induced by study drug(s) 	Prompt Report Form Copy of SAE Report to Sponsor Copy of subject's signed ICF	5 days
Unanticipated Adverse Device Event (UADE)	
 ◦ Guide wire breaks during insertion and cannot be retrieved ◦ Revision surgery to replace component ◦ Cardiovascular event induced by study device 	Prompt Report Form Copy of UADE (Device SAE) Report to Sponsor Copy of subject's signed ICF	5 days
SAE or UADE resulting in death	
 ◦ Any death related or possibly related to use of investigational drug or device 	Prompt Report Form Copy of SAE Report to Sponsor Copy of subject's signed ICF	24 hour phone notice 5 days: written report
Deaths within 30 days of study treatment (all others reported at continuing review)	
 ◦ Any death that occurs within 30 days of receiving study drug/device/intervention, regardless if PI determined death is "unrelated" and/or "expected" (this excludes MINIMAL RISK STUDIES such as registries or observational studies). 	Prompt Report Form Copy of SAE Report to Sponsor	5 days
Major Protocol Deviation/ Violation	
 ◦ Failure to obtain informed consent ◦ Omitting study procedure(s) required by-approved protocol ◦ Drug dispensing/dosing error ◦ Failure to securely control the study product ◦ Deviation necessary to eliminate an apparent immediate hazard to a participant 	Prompt Report Form	5 days
Research Complaint	
 ◦ Complaint from a participant regarding a research-related injury or study activities ◦ Complaint from study personnel regarding fabrication of data or research misconduct 	Prompt Report Form	5 days
Adverse Monitoring or Audit Reports, or Enforcement Action	
 ◦ Reports of study monitor visits or sponsor audits with findings that require action at this site to address potential risks to participants or others. ◦ Suspension or restriction of medical license ◦ FDA Form 483 or Warning Letter 	Prompt Report Form Copy of reports, audits, etc.	24 hour phone notice: suspensions or FDA 483 5 days: monitoring or audit reports
Other Unanticipated Problem	
 ◦ Participant becomes incarcerated ◦ Breach of participant confidentiality (e.g., breach of secured database) ◦ Study personnel misconduct that adversely affects the study 	Prompt Report Form	5 days
Recalls / Withdrawals / Clinical Holds	
 ◦ Correspondence communicating a Regulatory Agency or Sponsor mandated marketing recall, withdrawal, or clinical hold 	Prompt Report Form Copy of the correspondence	5 days
Reports, publications, or interim results or findings	
 ◦ DSBM reports and recommendations ◦ Regulatory Agency Public Health Advisory ◦ "Dear Healthcare Professional" Letter 	Prompt Report Form Copy of report, publication, interim finding, etc.	10 days
All Adverse Events (regardless if serious, related or expected) that do not meet Prompt Reporting criteria as described above	
 ◦ If applicable, a summary report of all adverse events should be provided to the IRB at least annually. ◦ The specific format of this report should be described in the Local Data Safety Monitoring Plan at the time of initial review. Many protocols will require only written verification on the Protocol Renewal Form (e.g. All adverse events have been reviewed by [the PI & study coord] and appear to be occurring at the frequency and intensity as is expected in this subject population) 	Protocol Renewal Form (if applicable)	Continuing review (if applicable)

